13.6. INTERIM ESTIMATION OF TREATMENT EFFICACY

This interim efficacy analysis will first evaluate whether the intervention is beneficial, equivalent, or harmful relative to usual care. A Bayesian logistic regression model will be fit to the data to obtain adjusted estimates of interim treatment efficacy, adjusting for the trial stratification variables.

A prior distribution is chosen in Bayesian analyses to provide an estimate of initial beliefs concerning the size of the potential treatment benefit. Thus, if one hopes that the results from the trial will influence the treatment of future patients, the prior distribution should represent the level of skepticism that is expressed by those clinicians that one seeks to influence. There are three principal types of prior we could use: (i) the uninformative, or reference prior, (ii) the skeptical prior and (iii) the enthusiastic prior. The uninformative prior represents a lack of clinical opinion as to the likely treatment difference, and in that sense contains no information about prior beliefs or other prior knowledge (eg. a relative risk for treatment benefit set at 1.0). A skeptical prior would be that overall effect of cord blood is actually harmful in this setting (i.e., a relative risk set higher than 1). An enthusiastic prior would be that the treatment is beneficial, as in the Phase I trial (relative risk set lower than 1).

It is generally useful to present the results of Bayesian analyses under several alternative prior distributions, so that the impact of differing levels of prior belief on the observed data may be reviewed. The uninformative prior has the advantage of corresponding roughly to the classical frequentist approach, and so this together with the skeptical and enthusiastic priors gives a broad and useful overview of the implications of terminating a clinical trial²⁷. Accordingly, we will use

A Phase II Multi-site Study of Autologous Cord Blood Cells for Hypoxic Ischemic Encephalopathy (HIE) IND 14753 (BABYBAC II)

all three prior distributions to present adjusted mean posterior relative risk (RR) estimates of treatment efficacy relative to survival free of cognitive impairment, along with corresponding 95% credible intervals for the same. These priors will be set at RR = 1.1 (skeptical prior), 1.0 (uninformative prior) and 0.625 (enthusiastic prior).

The DSMC may consider proposing termination of the trial for benefit if the upper 95% credible limit for the mean posterior RR of treatment benefit, calculated using a skeptical prior, is less than 1.0. We propose to use a skeptical prior for this consideration to provide a more conservative basis for trial termination, and also to convince even those who strongly believed at the outset that the intervention will not succeed in improving survival free of cognitive impairment. In addition, we note that early stopping of a trial based on treatment benefit generally produces a biased and sometimes misleading estimate of the treatment effect^{28, 29}.

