15.3. STATISTICAL ANALYSIS PLAN

All statistical analyses, including interim monitoring, will be conducted using the intent to treat principle, unless explicitly specified otherwise for certain secondary and/or post-hoc analyses. A Bayesian approach will be used for conducting the primary analysis in this trial. We propose to apply a log-binomial regression model and a neutral prior that will be centered at RR=1.0 to final

A Phase II Multi-site Study of Autologous Cord Blood Cells for Hypoxic Ischemic Encephalopathy (HIE) IND 14753 (BABYBAC II)

efficacy and safety data, where final data is defined as data contained in the study database after database lock. Database lock will occur either after 160 infants have completed the study or the study is terminated early for efficacy, futility, or safety. In addition to using a neutral prior, final analyses on locked data and some interim analyses will develop posterior distributions using skeptical (centered at $RR = 1.1$) priors and/or enthusiastic (centered at $RR = 0.625$) priors as well. In all analyses, MCMC methods will be used to sample from the Posterior distribution.

All analyses will involve estimating a Posterior distribution based on a log-binomial regression model with covariates and MCMC methods. In addition to estimating the treatment effect on the log relative risk scale, the log-binomial regression will adjust for level of encephalopathy. For the intercept and the encephalopathy terms, Normal (mean = 0, sd=100) priors will be used. For the term representing the log relative risk, skeptical, neutral, and enthusiastic priors will be used to estimate posterior distributions for the relative risk.

With respect to the primary efficacy endpoint, the estimated Posterior distribution of relative risk based on the data and the neutral prior will be used to determine posterior probabilities of >0 , >10 and $>20\%$ decrease in death or moderate/severe disability, as well as graphical displays of the Posterior distribution and appropriate 95% credible intervals for the relative risk. In addition to adjusting for level of encephalopathy and center in the log-binomial model, the final analysis of efficacy will also perform sensitivity analyses concerning possible treatment effect confounders present at randomization. All additional covariates added to the model will utilize Normal (mean=0, sd=100) priors.

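### Sections 13.6 and 15.3 name different models for the interim efficacy analysis, and nothing says how relative-risk priors enter the logistic one

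*Combined protocol and SAP*

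**What the plan says.** Section 13.6 names the interim model: "A Bayesian logistic regression model will be fit to the data to obtain adjusted estimates of interim treatment efficacy". The same section sets the prior centres on another scale: "These priors will be set at RR = 1.1 (skeptical prior), 1.0 (uninformative prior) and 0.625 (enthusiastic prior". It promises to use "all three prior distributions to present adjusted mean posterior relative risk (RR) estimates of treatment efficacy relative to survival free of cognitive impairment", with 95% credible intervals. The DSMC may consider proposing termination for benefit "if the upper 95% credible limit for the mean posterior RR of treatment benefit, calculated using a skeptical prior, is less than 1.0".

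Section 15.3 names a different model: "All analyses will involve estimating a Posterior distribution based on a log-binomial regression model with covariates and MCMC methods". It also says where the treatment prior sits: "For the term representing the log relative risk, skeptical, neutral, and enthusiastic priors will be used to estimate posterior distributions for the relative risk". It gives Normal priors with SD 100 for the intercept, the encephalopathy term and any added covariates. Neither section gives an SD for the treatment prior.

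**The concern.** A logistic coefficient is a log odds ratio and a log-binomial coefficient is a log relative risk. The two are close only when the outcome is rare. Here section 15.2 puts control failure (death or a Bayley III score below 85) at 0.6, so the same number means quite different effects on the two scales. Two statisticians following the plan in good faith could give the DSMC different posteriors from the same data, and they could disagree on whether the benefit criterion is met.

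Two priors are affected. The skeptical one drives the benefit rule. The enthusiastic one matters for futility, because section 13.7 primarily uses a prior set at the Phase I benefit. Section 13.7 names no model, so futility is affected only if it inherits the model of 13.6. The interim RR and the final RR would also come from different models.

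**Working it through.** **Inputs.** Control failure is 0.6 (15.2). Prior centres are 1.1, 1.0 and 0.625 (13.6). The benefit rule is an upper 95% credible limit below 1.0 under the skeptical prior (13.6). The look comes at one third of outcomes (13.5): 160/3 ≈ 53, about 27 per arm, or 120/3 = 40, which is 20 per arm. RR is read as the relative risk of failure, because 13.6 treats values below 1 as benefit. The treatment-prior SD is an assumption: 0.35, 0.5 or 1.0.

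**1. The scale of the plan's own design figures.** Exact binomial enumeration at 60 per arm, counting a win when the 95% interval for log RR excludes 0, compares with the 15.2 table as follows (control 0.6):

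| Cell-group failure | Power, stated | Power, computed | Width, stated | Width, RR | Width, OR |
|---|---|---|---|---|---|
| 0.30 | 0.92 | 0.924 | 0.45 | 0.458 | 0.501 |
| 0.35 | 0.81 | 0.803 | 0.48 | 0.489 | 0.616 |
| 0.40 | 0.62 | 0.612 | 0.51 | 0.517 | 0.753 |
| 0.45 | 0.38 | 0.393 | 0.54 | 0.542 | 0.920 |

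These four rows fit relative risks and not odds ratios. The null row fits less well: type I error computes to 0.050 against 0.056, and width to 0.606 (RR) or 1.736 (OR) against a printed 0.54. The prior and simulation behind the table are not given.

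**2. What the prior centres mean if placed on the logistic coefficient.** Control odds are 0.6/0.4 = 1.5. For an odds ratio OR, cell-group risk is 1.5·OR/(1 + 1.5·OR), and RR is that risk divided by 0.6.

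- OR 1.1: 1.65/2.65 = 0.623; RR = 1.04.
- OR 1.0: 1.5/2.5 = 0.600; RR = 1.00.
- OR 0.625: 0.9375/1.9375 = 0.484; RR = 0.81.

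The intended risk reduction of 1 − 0.625 = 0.375 becomes 1 − 0.806 = 0.194, about half. For control rates from 0.4 to 0.8, 0.625 read as an OR gives RR 0.74 to 0.89, and 1.1 gives RR 1.06 to 1.02.

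**3. Spread.** With SD 0.35 and centre 1.1, the 95% prior range is 1.1·exp(±1.96 × 0.35) = 0.55 to 2.18. Read as RR, that is the nominal range. Read as OR at control rate 0.6, it maps to RR 0.76 to 1.28. The same SD is therefore a tighter prior when placed on the odds scale.

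**4. Effect on the benefit rule.** The posterior was computed on a grid, unadjusted, with a near-flat intercept prior and a Normal(log 1.1, SD) prior on log RR or on log OR. The rule is met when the posterior probability of RR below 1 exceeds 0.975. All tables with 27 per arm were enumerated, with true failure 0.60 versus 0.30:

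| Assumed SD | Prior on log RR | Prior on log OR |
|---|---|---|
| 0.35 | 0.26 | 0.02 to 0.03 |
| 0.5 | 0.41 to 0.45 | 0.17 |
| 1.0 | 0.57 | 0.47 |

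Ranges reflect numerical sensitivity. At SD 0.5 on the RR scale, the tables with 15 versus 6 and 16 versus 7 failures have posterior probabilities of 0.9751 and 0.9764, almost on the threshold. Their combined probability is 0.0165 + 0.0239 = 0.040, the difference between 0.45 and 0.41.

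The direction is the same with a smaller effect or sample. For 0.60 versus 0.375 at SD 0.7, the chances are 0.316 versus 0.170 with 27 per arm and 0.207 versus 0.095 with 20 per arm. Under the null at SD 0.7 with 27 per arm, they are 0.019 versus 0.004.

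**The case against.** The strongest reply is that the priors need not change meaning at all. Section 13.6 states them as relative risks and section 15.3 puts them on the log relative risk. If 15.3 governs, they mean what they say. A logistic model can also carry a prior induced on the RR and return an RR by standardisation. This stands, so the shift in meaning is conditional on the values being placed directly on the logistic coefficient. But the plan describes no conversion step, which leaves that route open.

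Section 15.3 also reaches the interim less firmly than it first appears. The sentence "All statistical analyses, including interim monitoring, will be conducted using the intent to treat principle" extends the intent-to-treat principle to interim monitoring, not the model. Log-binomial regression is first proposed there for final data. The sentence that "final analyses on locked data and some interim analyses will develop posterior distributions using skeptical" and other priors concerns prior choice. What extends the model to the interim is the general sentence about all analyses. This is a specific statement against a general one, and the plan does not say which prevails.

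The consequence is also bounded. The DSMC may consider stopping but need not stop, it sees results under all three priors, and the final primary analysis is log-binomial with a neutral prior.

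A reader might infer that on the odds scale the skeptical prior no longer makes the benefit rule conservative. The calculation does not support that. Its centre is less skeptical, but for the same SD the rule becomes harder to meet. What is lost is chance of stopping when the benefit is real.

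**Conclusion.** The two sections contradict each other on the interim model, and the plan gives no bridge between the logistic model and its relative-risk priors, estimate and limit. That is wrong as written and should be corrected, because it can decide whether a stopping criterion is met.

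The documents do not support the broader statement that the stated priors fail to mean what they say. That holds only if the values sit directly on the logistic coefficient. The neutral centre and the limit of 1.0 are the same on both scales in any case. Under that condition, and at control failure 0.60, 1.1 becomes RR 1.04 and 0.625 becomes RR 0.81.

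The effect on stopping for benefit ranges from large at SD 0.35 to modest at SD 1.0, and the gap shrinks as the prior becomes vague. These probabilities rest on the assumed SDs, an unadjusted model, 27 per arm and a true 0.60 versus 0.30. The effect on futility stopping was not calculated, so only the shift in the enthusiastic centre can be claimed there.

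**What to change.** In section 13.6, replace the logistic model with the log-binomial model of 15.3. Put the skeptical, neutral and enthusiastic priors on log RR, keep the encephalopathy term, and state the SD of the treatment prior in both sections. The SD is essential: without it the prior is undefined under either model. Say in 13.7 that futility uses the same model. Interim and final relative risks would then come from one model.

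If logistic regression is kept as a fallback for non-convergence, state that the prior is induced on the RR and that the RR is obtained by standardising over encephalopathy level. Do not substitute fixed odds ratios. RR 0.625 needs OR (0.3125/0.6875)/(0.5/0.5) = 0.45 at control failure 0.5, but (0.4375/0.5625)/(0.7/0.3) = 0.33 at 0.7. If failure rates differ between moderate and severe strata, one OR cannot represent one RR in both.

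The cost is a short text change with no effect on data collection or sample size. It should be made before anyone sees unblinded interim outcome data.

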13.7. INTERIM ESTIMATION OF TREATMENT FUTILITY

In addition to providing estimates of interim treatment efficacy, we will also conduct interim futility analyses for treatment efficacy. For this purpose, at each interim safety look, we will use the available data to calculate the posterior probability of concluding that the probability of survival free of cognitive impairment in the cord blood group would be higher than in the placebo group (i.e., the mean posterior RR for treatment benefit is greater than 1.0), if the trial continued until 120 patients were randomized and had their primary outcomes evaluated. In order to provide a more conservative basis for this estimate, and also to convince even those who strongly believed in this intervention at the outset, we will primarily use an optimistic prior for this calculation, with the prior belief set at a level of treatment benefit observed in the Phase I trial. However, in order to provide a broad overview and to explore the robustness of this estimate with respect to prior assumptions, this probability will also be calculated and presented for the two other prior distributions (skeptical and uninformative).

The DSMC may consider proposing termination of the trial for futility if this posterior probability of observing any treatment benefit, if the trial continued to full primary outcome accrual, is less than 10%.

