15.2. ESTIMATES OF AVAILABLE AND REQUIRED SAMPLE SIZE

In our phase I study to date, 16 of 25 (64%) cell recipients with known one year outcomes have survived with all three Bayley III assessments (Cognitive, Motor, and Language) ≥ 85 , and 25 of 63 (40%) of the cooled-only infants with known one year outcomes has survived with all three Bayley III domain scores ≥ 85 . (13) We acknowledge the limitations of a one year Bayley score, but would note that our rate of survival with Bayley scores ≥ 85 among cooled-only infants is consistent with the previously reported Whole Body Hypothermia studies rates of survival at 12–24 months without moderate or severe impairment (1 -4).

For the phase II study, rather basing the sample size on effect size, we would propose a Bayesian approach as used in the NRN Late Hypothermia study. Because this is phase II where our aim is to detect a trend favoring cell recipients, and to accumulate data that will inform design and sample size calculations for a phase III study of efficacy, we anticipate that two years of enrollment would provide approximately 120-160 infants, 60-80 in each group.

Control	Cell Recipients	95% Confidence Interval	Power
0.6	0.30	0.45	0.92
0.6	0.35	0.48	0.81
0.6	0.40	0.51	0.62
0.6	0.45	0.54	0.38
0.6	0.60	0.54	0.056

The Bayesian analysis will permit calculation of a probability of treatment benefit. Within the range of an active group proportion of 0.3 to 0.45, the average 95% credible interval width ranges from 0.45 to 0.54 when the control group has a proportion having the primary outcome (death or Bayley III scores < 85) of 0.6. If the decision rule for declaring a win is the posterior 95% credible interval must exclude 1, then the design has power ranging from 0.92 to 0.38 with a Type 1 error of about 0.056.

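### Sections 13.6 and 13.7 use the relative risk on opposite scales, so the futility rule is reversed if its inequality is coded with the stated priors; define RR once.

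*Combined protocol and SAP*

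**What the plan says.** **Section 13.6** fixes the direction of RR three times.
- The skeptical prior is that the "overall effect of cord blood is actually harmful in this setting (i.e., a relative risk set higher than 1".
- For the opposite view: "An enthusiastic prior would be that the treatment is beneficial, as in the Phase I trial (relative risk set lower than 1".
- The centres follow: "These priors will be set at RR = 1.1 (skeptical prior), 1.0 (uninformative prior) and 0.625 (enthusiastic prior".

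Its stopping rule for benefit requires that the "upper 95% credible limit for the mean posterior RR of treatment benefit, calculated using a skeptical prior, is less than 1.0". The same section nevertheless labels these RRs as "estimates of treatment efficacy relative to survival free of cognitive impairment", which is a favourable outcome.

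**Section 13.7** defines the futility event as a higher probability of impairment-free survival in "the cord blood group would be higher than in the placebo group (i.e., the mean posterior RR for treatment benefit is greater than 1.0". It uses mainly an optimistic prior set at the Phase I benefit, and also presents the skeptical and uninformative priors. The DSMC may consider stopping if the probability is below 10%.

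**Sections 15.2 and 15.3** work with the adverse outcome. Section 15.2 takes "a proportion having the primary outcome (death or Bayley III scores < 85) of 0.6" in controls. Section 15.3 reuses the centres 1.1, 1.0 and 0.625 and seeks a "decrease in death or moderate/severe disability". Section 11.5 states the primary outcome favourably, as survival with all three scores at least 85.

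No section gives the outcome, numerator and denominator of RR together. Section 15.3 gives an SD (100) for the intercept and covariate priors, but none for the treatment term.

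**The concern.** The benefit rule and the futility rule go to the same DSMC, apply to the same endpoint and draw on the same named priors, yet benefit lies below 1 in one and above 1 in the other. A programmer who takes RR and the priors from 13.6 and the inequality from 13.7 would compute the probability that cord blood ends up worse, and would raise a futility flag when that probability is small. The flag would then appear mainly when the treatment works, and a trial meeting the benefit rule could be reported as futile at the same look.

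**Working it through.** **1. The plan's own figure.** Phase I success (sections 5.2 and 15.2) was 64% with cells (16/25) and 40% with cooling alone (25/63).
- Survival ratio, cells/control: 0.64/0.40 = 1.6
- Survival ratio inverted: 0.40/0.64 = 0.625, which is the stated enthusiastic centre
- Adverse-outcome ratio, cells/control: 0.36/0.60 = 0.60

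The centre 0.625 is therefore reproduced exactly as an inverted survival ratio. It is close to the Phase I adverse-outcome RR but not equal to it. Benefit is below 1 on both of those scales. It is above 1 only on the cells/placebo survival scale, where the matching prior would be 1.6.

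**2. Which scale 15.2 uses.** The approximate 95% interval width is RR × (e^(1.96·SE) − e^(−1.96·SE)). Take 60 per arm and the first table row (adverse proportions 0.60 and 0.30).
- Adverse-outcome RR = 0.50; SE = √[(0.7/0.3 + 0.4/0.6)/60] = 0.224; width 0.45. The table says 0.45.
- Survival RR = 0.70/0.40 = 1.75; SE = √[(0.3/0.7 + 0.6/0.4)/60] = 0.179; width about 1.26.
- Inverted survival RR = 0.571, same SE; width about 0.41.

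Power for the adverse-outcome RR (exact enumeration, Wald 95% interval for log RR excluding 0) agrees at 60 per arm:

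| Adverse proportion, cells | Table | 60 per arm | 80 per arm |
|---|---|---|---|
| 0.30 | 0.92 | 0.92 | 0.97 |
| 0.35 | 0.81 | 0.80 | 0.89 |
| 0.40 | 0.62 | 0.61 | 0.72 |
| 0.45 | 0.38 | 0.39 | 0.47 |

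The adverse-outcome ratio fits 15.2, the benefit rule in 13.6 and the stated aim of 15.3. The table corresponds to 120 infants, not 160.

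**3. Effect of literal coding.** Assumptions: placebo failure 0.60, cells 0.40, normal prior on log RR centred at log 0.625, prior SD 0.35-1.0 (assumed). The formal look is at a third of outcomes: 20 per arm if the final N is 120, about 27 if it is 160.

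Formulas, with 0.5 added per cell: interim log RR *l* with variance *v*; prior mean *m0* and variance *s²*.
- Posterior variance v1 = 1/(1/v + 1/s²); posterior mean m1 = v1(l/v + m0/s²)
- Posterior variance at final N: vf = 1/(k/v + 1/s²), where k = final n / interim n
- Predictive distribution of the final posterior mean: N(m1, v1 − vf)

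Worked case, 8/20 against 12/20 failures, SD 0.5, k = 3:
- l = log(8.5/12.5) = −0.386; v = 1/8.5 + 1/12.5 − 2/21 = 0.102
- v1 = 0.0726; m1 = −0.410 (RR 0.66); vf = 0.0300; predictive SD = √(0.0726 − 0.0300) = 0.206
- P(final mean RR < 1) = Φ(0.410/0.206) = 0.98, so the intended rule does not flag
- P(final mean RR > 1) = 0.02, below 10%, so the literal rule flags futility

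Over 200,000 simulated trials per setting, with cells working:

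| Interim to final | Literal flag | Intended flag | 13.6 benefit rule met (prior 1.1) |
|---|---|---|---|
| 20 per arm to 120 | 60-89% | at most 0.5% | 0.3-13% |
| 27 per arm to 160 | 70-90% | at most 0.4% | 3-21% |

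Every trial that met the benefit rule also tripped the literal flag, and none tripped the intended one. With the neutral and skeptical priors at 20 per arm, the literal rule flags 38-57% and the intended rule under 1%, so the reversal does not come from the enthusiastic prior.

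**4. Secondary points.** Section 13.7 projects to 120 infants and treats that as full outcome accrual; 15.3 locks at 160. At 27 per arm, the choice between the two moves the literal figures by up to about 8-10 points. Section 13.7 also places futility at each safety look (every 40 infants, 13.4), while 13.5 plans one formal look. At the projected 60-80 infants a year, the first 40 are enrolled by month 6-8 (12 × 40/80 to 12 × 40/60), before any 12-month Bayley score exists. Deaths would already be known.

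**The case against.** The strongest defence is that 13.7 is coherent by itself. It names survival free of impairment, compares cord blood with placebo, and equates a higher probability with RR above 1. It does not quote 0.625, and 11.5 also states the outcome favourably. That stands: the defect is two unharmonised scales, not necessarily a slip in one inequality, and a survival ratio with inverted priors and an inverted benefit rule would also reconcile the text. But 13.7 sets up no scale or centres of its own. It relies on the three priors of 13.6, and a Phase I prior on a survival scale would be 1.6.

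It is also fair that the percentages describe someone who codes the parenthesis and ignores both the clause it explains and the action sentence about any treatment benefit. Part of the result is algebra: a literal flag requires a posterior that favours cells.

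A reader might infer that the trial would probably be stopped while the treatment is working. The documents do not support that. The verbal criterion is right, the DSMC only may consider stopping, and it would see an RR favouring cells beside the flag. The DSMC charter, which could settle the direction, is not among the documents. Nor is the final analysis affected, because 15.3 does not use this inequality.

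**Conclusion.** The contradiction is in the current text and should be fixed before any interim analysis is programmed. On the scale of the stated priors, the 13.7 event is harm, and literal coding reverses the rule. The direction of the conflict rests on no assumption. The size does: the 60-89% and 70-90% figures depend on the assumed prior SD, the normal approximation and a true failure rate of 0.40 against 0.60. They should not be read as the chance of a wrong stop. What is shown is an avoidable programming and interpretation risk in an advisory rule. Reversing the inequality alone is not enough, because 13.6 attaches below-1 priors to a favourable outcome and 0.625 is not the Phase I adverse-outcome RR. The final N and the look timing are lesser inconsistencies to settle in the same edit.

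**What to change.** - Define RR once for 13.6, 13.7 and 15.3: risk of death or any Bayley-III domain below 85, cells divided by placebo, with benefit RR < 1. Use that outcome in place of the disability wording in 15.3.
- In 13.7, change the inequality to less than 1.0 and keep the 10% limit.
- In 13.6, replace the reference to survival free of cognitive impairment with the adverse outcome above.
- State the centre and SD of each treatment prior on this scale. Either describe 0.625 as the inverted Phase I survival ratio (0.40/0.64) or use the Phase I adverse-outcome RR of 0.60.
- In 13.4, harm is a probability that theta exceeds 1, but theta is described as a relative risk in favour of treatment. Define it as the cells/placebo relative risk of the listed adverse events.
- Secondary: make the projection N in 13.7 agree with the lock in 15.3, and reconcile futility at every safety look with the one formal look in 13.5. If early looks stay, say that they will hold deaths but no 12-month Bayley scores.

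The cost is wording in 13.4, 13.6, 13.7 and 15.3, plus alignment of the DSMC charter. No patients, visits or procedures are added, and the number of futility looks remains the sponsor's choice.
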